### **9.2.2. Vital Signs, Height, and Weight**

Blood pressure (standing and supine), heart rate, respiration rate, temperature, weight, and BMI will be collected at screening, Day 1, Day 8, and Day 56. Height will be collected at screening only. A summary of change from baseline in the vital signs at baseline and all scheduled post-baseline visits will be provided.

A listing of vital signs will also be provided.

### **9.2.3. Electrocardiogram**

A standard 12-lead electrocardiogram (ECG) will be performed on Day 1 prior to dosing, Day 8, and Day 56. A summary for change from baseline in the ECG parameters (Ventricular Rate, PR Interval, RR Interval, QRS Interval, QT Interval, QTcB Interval, QTcF Interval) at baseline and all scheduled post-baseline visits will be provided.

The ECG results are to be interpreted as follows: Normal; Abnormal, NCS (not clinically significant); Abnormal, CS (clinically significant). A shift table of the interpretation will

be presented for all scheduled post-baseline visits. Categories for the shift table will be as follows: Missing; Normal; Abnormal, NCS; Abnormal, CS; Total.

Additionally, a categorical summary of maximum post-baseline QTcB Interval ( $> 0$  to  $<= 500$  msec,  $> 500$  msec), maximum post-baseline QTcF Interval ( $> 0$  to  $<= 500$  msec,  $> 500$  msec), and maximum change from baseline ( $> 0$  to  $< 30$  msec,  $>= 30$  to  $<= 60$  msec,  $> 60$  msec) for both QTcB and QTcF will be provided.

A listing of ECG data will also be provided.

#### **9.2.4. Clinical Laboratory Tests**

Laboratory evaluations (hematology, serum chemistry, coagulation, urinalysis) will be conducted at Screening, Day 1, Day 8, Day 56, and Day 70. Any clinically significant laboratory result after baseline is to be captured as an adverse event and thus included in the summary of adverse events.

Summary statistics for the observed and change from baseline continuous laboratory results will be displayed at baseline and all scheduled post-baseline visits via the following tables:

- Hematology
- Serum Chemistry
- Coagulation
- Urinalysis

For categorical urinalysis results, frequency counts and percentages will be presented.

For laboratory parameters (hematology, serum chemistry, coagulation) where normal ranges are available, shift tables will be presented for all scheduled post-baseline visits. Categories for the shift tables will be Missing, Low, Normal, High, and Total.

A listing for each category of laboratory results shown in the above bulleted list as well as a listing for serology will also be provided, and values will be flagged as Low, Normal, or High relative to normal ranges, if available, and included in the listings. In addition, a listing will be provided for urine drug screen results and a listing will be provided for alcohol breath test screen results.

#### **9.2.5. Physical Examination**

A physical examination (PE) will be conducted during the screening period and at end of treatment. Any abnormalities noted prior to first administration of the investigational

product are to be captured as medical history. Findings after first administration of the investigational product that meet the criteria of an AE are to be captured as an AE.

A listing of PE results will be provided. No summary tables will be provided.

#### **9.2.6. Lens Opacities Classification System III (LOCS III)**

An ophthalmic exam including slit-lamp imaging may be performed and would be assessed using LOCS III. Any result that is an AE of Special Interest as defined in Section 5.2 of this SAP is to be recorded.

LOCS III data are collected at Screening, Day 56, Day 70, and Day 112. A summary for change from baseline in four LOCS III parameters (Cortical Lens Opacity, Nuclear Color, Nuclear Opalescence, Posterior Subcapsular Lens Opacity) by eye (OD, OS) at all scheduled post-baseline visits will be provided.

In addition, a shift table for each of the LOCS III parameters by eye will be provided. The possible values for Cortical Lens Opacity (C) range from 0.1 to 5.9, for Nuclear Color (NC) range from 0.1 to 6.9, for Nuclear Opalescence (NO) range from 0.1 to 6.9, and for Posterior Subcapsular Lens Opacity (P) range from 0.1 to 5.9. The exclusion criteria based on LOCS III are as follows:

- C with a LOCS III classification > 2.0 in either eye
- NC with a LOCS III classification > 3.5 in either eye
- NO with a LOCS III classification > 3.0 in either eye
- P with a LOCS III classification > 0.3 in either eye

Given the above exclusion criteria and the definition of AEs of Special Interest as provided in Section 5.2 of this SAP, the categories for the shift tables will be defined as follows, where Nuclear Color will follow the same shift table categorization strategy as Nuclear Opalescence, Cortical Lens Opacity, and Posterior Subcapsular Lens Opacity:

Baseline categorization:

- C: Missing, 0.1 to <= 1.0, > 1.0 to <= 2.0, > 2.0, Total
- NC: Missing, 0.1 to <= 1.5, > 1.5 to <= 2.5, > 2.5 to <= 3.5, > 3.5, Total
- NO: Missing, 0.1 to <= 1.0, > 1.0 to <= 2.0, > 2.0 to <= 3.0, > 3.0, Total
- P: Missing, 0.1 to <= 0.2, > 0.2 to <= 0.3, > 0.3, Total

Post-baseline categorization:

- Change: Missing, <= -0.5, > -0.5 to < 0, No Change, > 0 to < 0.5, >= 0.5, Total

Primary ophthalmic data (assessment of first reading) will be used for summaries, and a listing of primary ophthalmic data will also be provided. Secondary ophthalmic data (secondary readings) will not be summarized or listed.

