9.4.2. Analysis of Safety

The Safety Population will be used to provide descriptive summaries of safety data. Treatment-emergent adverse events will be classified by type, incidence, severity, and causality. The overall incidence of adverse events will be summarized by Medical Dictionary for Regulatory Activities (MedDRA) System Organ Class (SOC) and Preferred Term (PT). Data for vital signs, clinical laboratory tests, ECG, physical examinations, and concomitant medication usage will also be summarized.

Changes in LOCS III will be assessed from Screening to Day 56, 70 and 112 visits. An increase from baseline in the LOCS III grade of \geq 0.5 (Nuclear Opalescence), \geq 0.5 (Cortical) or \geq 0.5 (Posterior Subcapsular)] in either eye and any changes considered to be clinically significant

(e.g., incidence of cataract) as per the ophthalmologist or optometrist will be reported as an adverse event and an event of special interest.

Suicidality data collected using the C-SSRS at baseline and at each visit during the active Open-Label Treatment Period will be listed for all subjects. The C-SSRS listings will include behavior type and/or category for suicidal ideation and suicidal behavior of the C-SSRS.

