### 9.2.1. Adverse Events

Adverse events (AEs) summaries will only consider treatment-emergent adverse events (TEAEs), using the safety population. TEAEs are defined as those AEs that occurred after dosing and those existing AEs that worsened during the study. If it cannot be determined whether the AE is treatment-emergent due to an incomplete or missing onset date or time, the AE will be considered a treatment-emergent AE. AEs with an onset day after the last day study medication was applied will not be considered TEAEs.

An overall categorical summary of TEAEs will be provided where the total number of TEAEs, the number and percent of subjects with at least one mild, moderate, or severe TEAE, and the number and percent of each of the following items will be displayed:

- Subjects with at Least One TEAE
- Subjects with at Least One TEAE Related to Study Treatment
- Subjects with at Least One TEAE Leading to Discontinuation of Study Treatment

- Subjects with at Least One TEAE of Special Interest
- Subjects with at Least One Serious TEAE
- Subjects with at Least One TEAE Leading to Death

AEs of Special Interest and Related AEs are defined as stated in Section 5.2 of this SAP. If a subject reports one or more events within the same SOC and PT, the subject is classified (Related/Not Related) according to the most related relationship within the same SOC and PT.

In addition, for each bulleted item in the above list, categorical summaries for TEAEs by system organ class (SOC) and preferred term (PT) via MedDRA version 25.0 will be provided, and subjects having more than one TEAE may appear in more than one SOC or PT but will be counted at most once per each SOC and PT. Furthermore, a summary of TEAEs by SOC, PT, and maximum relatedness (Related, Not Related) will be provided where the maximum relatedness will be used for subjects with multiple TEAEs within the same SOC and PT, and a summary of TEAEs by SOC, PT, and maximum severity (Mild, Moderate, Severe) will be provided where the maximum severity will be used for subjects with multiple TEAEs within the same SOC and PT. Summaries that are displayed by SOC and PT will be ordered by descending incidence of SOC and then PT within each SOC, and if applicable ascending severity within SOC and PT.

A listing of adverse events and a listing of serious adverse events will also be provided.

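### No planned summary table counts the subjects with a LOCS III increase of 0.5 or more in either eye at any post-baseline assessment

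*SAP*

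**What the plan says.** **Event.** Protocol 9.4.2 says LOCS III change is assessed from Screening to Days 56, 70 and 112. It makes an increase of 0.5 or more in any of three grades, "in either eye and any changes considered to be clinically significant", an adverse event and an event of special interest. SAP 5.2 uses the same three grades and the same 0.5 threshold, adds other clinically significant ophthalmic results, and does not mention the eye. LOCS III is a primary safety parameter in Protocol 3 and SAP 9.1.

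**Tables.** In SAP 9.2.6, "LOCS III data are collected at Screening, Day 56, Day 70, and Day 112". The change summary covers four parameters "by eye (OD, OS) at all scheduled post-baseline visits will be provided". The second tabular output is split in a similar way: "a shift table for each of the LOCS III parameters by eye will be provided", with these post-baseline categories: "Change: Missing, <= -0.5, > -0.5 to < 0, No Change, > 0 to < 0.5, >= 0.5, Total". The shift-table sentence does not say whether there is one table per visit.

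**Listing.** SAP 9.2.6 also states that "a listing of primary ophthalmic data will also be provided", while "Secondary ophthalmic data (secondary readings) will not be summarized or listed". SAP 9 says safety results are listed by subject, and SAP 10 sorts listings by subject and visit.

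**Adverse events.** SAP 9.2.1 plans a row for "Subjects with at Least One TEAE of Special Interest". The same section removes from the TEAE definition any event whose onset falls after the last day of study medication. Listings of AEs and SAEs are planned and are not confined to TEAEs.

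**The concern.** The lens event belongs to a subject, because a qualifying change in one eye, in one grade, at one visit is enough. The tables count within a single parameter and eye, and the change summary also within a visit. One subject can appear in several cells, and several subjects can appear in one cell each, so the cells do not say how many people were affected.

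That number is the natural safety result here. Lens opacity is the only event of special interest named in Protocol 8.4.9. Protocol 2.4 reports that the earlier Phase 2 study had two such events, in two subjects, both in the 50 mg group. With counts this small, uncertainty of one or two subjects matters to a reader comparing the two studies.

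The special-interest row in SAP 9.2.1 looks like the missing count, but its time window is narrower than the LOCS III schedule.

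**Working it through.** The plan states no expected lens-event rate and no sample-size calculation, so there is no planned figure to reproduce. Two checks apply.

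**1. Do the planned tables determine the number of affected subjects?**

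Inputs:
- 3 event-defining grades, or 4 with Nuclear Color (SAP 5.2 and 9.2.6)
- 2 eyes
- 3 scheduled post-baseline visits: Days 56, 70 and 112
- N = 20, the stated maximum (SAP 6.1)
- Assumption: the shift tables are produced per visit, which the SAP does not say

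Number of cells with a count of changes of 0.5 or more: 3 × 2 × 3 = 18 for the event-defining grades, and 4 × 2 × 3 = 24 with Nuclear Color.

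Let x_j be the number of subjects at 0.5 or more in cell j. The number of distinct subjects D satisfies

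max(x_j) ≤ D ≤ min(N, Σ x_j).

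| Illustrative cell counts | Range for D | Share of 20 | Exact 95% CI at lower and upper end |
|---|---|---|---|
| All 18 cells zero | 0 | 0% | 0 to 16.8% |
| One cell = 1, rest zero | 1 | 5% | 0.1 to 24.9% |
| One grade, one visit: right 2, left 2 | 2 to 4 | 10% to 20% | 1.2 to 31.7%; 5.7 to 43.7% |
| One grade: 1 in each eye at each of 3 visits | 1 to 6 | 5% to 30% | 0.1 to 24.9%; 11.9 to 54.3% |
| 1 in each of the 18 cells | 1 to 18 | 5% to 90% | 0.1 to 24.9%; 68.3 to 98.8% |

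The third row can be shown directly. If subjects 1 and 2 each change in both eyes, the cells read right 2, left 2, with 2 subjects affected. If subjects 1 and 2 change in the right eye and subjects 3 and 4 in the left, the cells are the same, with 4 affected. The count is settled only in simple cases, such as all cells zero or one non-zero cell. The baseline rows of the shift tables may narrow a range but do not settle it in general.

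**2. Does the special-interest row in SAP 9.2.1 supply the count?**

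- Protocol 4.1: the last dose is taken at the Day 56 visit.
- SAP 9.2.1: onset after the last dosing day means the event is not a TEAE.
- SAP 9.2.6: LOCS III is graded at Days 56, 70 and 112.

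If onset is dated to the visit at which the change is first seen, changes first seen at Day 70 or Day 112 are not TEAEs. The row then covers 1 of the 3 scheduled visits, even if sites report every change. For subjects who stop early, footnote a of the Schedule of Events places the Day 56 procedures after discontinuation, so that visit can also fall outside the window.

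**Other outputs.** Protocol 8.4.9 allows extra slit-lamp imaging during treatment, but SAP 5 builds tables from scheduled visits, so those readings may enter no LOCS III table. The listing holds at most 20 × 18 = 360 scheduled post-baseline values for the three grades (20 × 24 = 480 with Nuclear Color), so a hand count is feasible.

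**The case against.** The strongest reply is that nothing is lost. Primary readings are listed by subject, there are at most 20 subjects, and a reader can count them. This stands, and it limits the point. A reader might infer from the tables that the count cannot be recovered from the measured data at all; the planned listing shows otherwise. What remains is that a hand count has no pre-specified denominator and no rule for unscheduled readings. SAP 5 labels analyses added after database lock as post hoc.

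A second reply is that the protocol already requires each qualifying change to be reported as an AE, so the AE outputs carry the count. It is tempting to answer that sites may miss central readings. No passage suggests this should be expected, and the point does not need it: the TEAE window alone leaves the row incomplete. The reply is right that AEs are recorded to Day 112 (Protocol 8.4.3) and that the AE listing is not limited to TEAEs. But that is again a listing and not a summary.

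Third, Protocol 9.4.2 sets a reporting rule and does not ask for a proportion of subjects. This is correct. The SAP does not breach the protocol here; it omits a useful summary. The SAP already takes a maximum post-baseline value for QTcB and QTcF in 9.2.3, so a summary across visits would not be foreign to it.

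Finally, the cell counts in the table above are invented. They show that the tables leave the number open, not what the trial will find.

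**Conclusion.** The point holds as a gap in the summary tables, and it is minor. No planned table reports how many subjects had an increase of 0.5 or more in any of the three event-defining grades, in either eye, at any post-baseline assessment. The one subject-level row leaves out changes first dated at two of the three scheduled post-baseline LOCS III visits.

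The possible ambiguity is a few subjects out of 20, for example 2 to 4, which is comparable with the two subjects behind the earlier signal. This rests on N = 20, on shift tables being produced per visit, and on onset being dated to the visit at which the change is first seen. The gap affects how completely a primary safety parameter is presented. It changes no hypothesis test, since the protocol plans none, and the underlying readings remain available.

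**What to change.** In SAP 9.2.6, add one table derived from the primary LOCS III readings and independent of TEAE status:

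- n/N (%) of subjects with an increase of 0.5 or more in Nuclear Opalescence, Cortical or Posterior Subcapsular grade in either eye.
- One row for each scheduled visit, and one for any post-baseline assessment through Day 112, stated to include unscheduled imaging.
- N is subjects with a baseline and at least one post-baseline grade. Show the number graded at each visit beside the visit rows.

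Add a short listing of subjects who meet the threshold without an AE of special interest on record, and of subjects with such an AE who do not meet the threshold. Mark those who qualify only because a change was judged clinically significant, since they are legitimate events and not discrepancies. State in the same section whether the shift tables are produced per visit.

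The cost is SAP wording, one derived flag, one table and one short listing. No new data or visits are needed.

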#### **9.2.7. Columbia-Suicide Severity Rating Scale (C-SSRS)**

The Columbia-Suicide Severity Rating Scale (C-SSRS) will be used to assess suicidal ideation and behavior. The “Baseline/Screening” C-SSRS form will be completed at screening. The “Since Last Visit” C-SSRS form will be completed at all other visits (Day 1, Day 8, Day 15, Day 29, Day 43, Day 56, Day 70).

The “Baseline/Screening” C-SSRS form contains the following possible types of responses per each item: response based on Past Month, response based on Life, and/or Describe event. The “Since Last Visit” C-SSRS form contains the following possible types of responses per each item: response based on Since Last Visit and/or Describe event. Not all types of responses are present for all items.

C-SSRS Suicidal Ideation contains the following five ordered Yes/No response items:

1. Wish to be Dead
2. Non-Specific Active Suicidal Thoughts
3. Active Suicidal Ideation with Any Methods (Not Plan) without Intent to Act
4. Active Suicidal Ideation with Some Intent to Act, without Specific Plan
5. Active Suicidal Ideation with Specific Plan and Intent

C-SSRS Intensity of Ideation contains the following six numeric response items:

- Most Sever Ideation (1-5)
- Frequency – How many times have you had these thoughts (1-5)?
- Duration – When you have the thoughts how long do they last (1-5)?
- Controllability – Could/can you stop thinking about killing yourself or wanting to die if you want to (1-6)?
- Deterrents – Are there things - anyone or anything (e.g., family, religion, pain of death) - that stopped you from wanting to die or acting on thoughts of committing suicide (1-6)?
- Reasons for Ideation – What sort of reasons did you have for thinking about wanting to die or killing yourself? Was it to end the pain or stop the way you were feeling (in other words you couldn’t go on living with this pain or how you were feeling) or was it to get attention, revenge or a reaction from others? Or both (1-6)?

The Suicidal Ideation Subscale Score is determined as follows. For the five C-SSRS Suicidal Ideation items, Yes/No responses are recorded. The maximum item number where Yes is the response is the Suicidal Ideation Subscale Score, i.e., the most severe ideation endorsed is the score. Zero is to be assigned (a) if all responses to Categories 1-5 are No or (b) if responses to Categories 1-2 are both No and responses to Categories 3-5 are missing. If a score is not able to be determined, then it will be left as missing.

The Intensity of Ideation Subscale Score is determined as follows. The sum of responses on five C-SSRS Intensity of Ideation items (Frequency, Duration, Controllability, Deterrents, Reasons for Ideation) is the Intensity of Ideation Subscale Score. If the Suicidal Ideation Subscale Score is zero or missing, the Intensity of Ideation Subscale Score is also zero or missing, respectively. Higher values for the Intensity of Ideation Subscale Score indicate more intense ideation.

Summary statistics for the Suicidal Ideation Subscale Score and Intensity of Ideation Subscale Score from the “Baseline/Screening” C-SSRS form and “Since Last Visit” C-SSRS form will be presented by scheduled visit, where the screening visit will contain Past Month and Life summaries and other scheduled visits will contain the Since Last Visit summary.

A shift table of Suicidal Ideation Items 1 and 2 (Wish to be Dead, Non-Specific Active Suicidal Thoughts) will be presented using “Since Last Visit” for all scheduled post-baseline visits. Categories for the shift table will be Missing, No, Yes, and Total.

A listing of C-SSRS Suicidal Ideation and C-SSRS Intensity of Ideation will be provided. The Suicidal Ideation Subscale Score and Intensity of Ideation Subscale Score will be included in the listing.

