3. OBJECTIVES AND ENDPOINTS

Objectives	Endpoints
Primary	
To evaluate the effect of treatment with ANC-501 capsules on depressive symptoms in subjects with major depressive disorder (MDD)	Change from baseline (Day 1) to Day 56 in Montgomery-Åsberg Depression Rating Scale (MADRS) total score
To evaluate the safety and tolerability of ANC-501 capsules in subjects with MDD	Safety and tolerability as assessed by: Frequency and severity of adverse events (AEs) Vital signs Body weight Electrocardiograms (ECGs) Clinical laboratory tests Physical examination Lens Opacities Classification System III (LOCS III) Emergent Suicidal behavior using Columbia-Suicide Severity Rating Scale (C-SSRS)
Secondary	
 To evaluate effect of ANC-501 at all time points and percent reduction in total symptom scores compared with baseline. To assess the pharmacokinetic (PK) profile of ANC 501 Capsules in plasme. 	 Change from baseline (Day 1) in the MADRS total score at all time points Percentage of MADRS responders (≥50% reduction in total score) Percentage of MADRS remitters (total score ≤10) Change in Hamilton Anxiety Scale (HAM-A) total score from Baseline to Day 56 Change in Clinical Global Impression-Severity (CGI-S) score from Baseline to Day 56 Short Form-Health Survey (36-item) (SF-36) total score and subscale scores from Baseline to Day 56 and at all time points Percentage of Clinical Global Impression-Improvement (CGI-I) improvers ("Very much improved" or "Much improved") Patient Global Impression of Improvement (PGI-I) score at Day 56 Plasma concentrations of ANC-501
profile of ANC-501 Capsules in plasma using a sparse sampling model	
Exploratory	
• To evaluate changes in 12-hour urine, plasma, and saliva cortisol	Changes in 12-hour urine, plasma, and saliva cortisol from baseline to Day 56
• To evaluate changes in biometrics	Changes in biometrics using the wearable watch-like device
 To evaluate biological samples as potential biomarkers and metabolites Patient reported changes in Depression and Anxiety symptoms 	 Baseline levels and/or changes in exploratory biomarkers through Day 56 Changes in Hamilton Depression Rating Scale (6-item) (HAMD-6) scores from baseline across all time points using ePRO
	Changes in General Anxiety Disorder (7-item) (GAD-7) from baseline across all time points using ePRO

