8.4.3. Time Period for Collecting AE and SAE Information

All AEs will be recorded from study drug administration on Day 1 until Day 112 (see Section 8.3.1.1 regarding laboratory-associated AE assessments).

Serious adverse events that occur subsequent to the signing of the informed consent (i.e., during the Screening Period) as a result of study participation will be recorded, as well as all SAEs occurring from study drug administration on Day 1 until Day 112. If the Investigator becomes aware of an SAE that is possibly related to the investigational drug treatment at any time after the final follow-up visit, the Sponsor should be notified immediately (i.e., within 24 hours). Report the SAE using the method described below.

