## 9.1. Safety Parameters

Primary parameters for safety to be considered include:

- Frequency and severity of adverse events (AEs)
- Vital signs
- Body weight
- Electrocardiograms (ECGs)
- Clinical laboratory tests
- Physical examination
- Lens Opacities Classification System III (LOCS III)
- Emergent behavior using Columbia-Suicide Severity Rating Scale (C-SSRS)

The secondary safety parameter is the plasma concentrations of ANC-501.

Exploratory parameters for safety to be considered include:

- Changes in 12-hour urine, plasma, and saliva cortisol from baseline to Day 56
- Changes in biometrics using the wearable watch-like device
- Baseline levels and/or changes in exploratory biomarkers through Day 56

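### Emergent suicidal behavior on the C-SSRS is a primary safety endpoint, but none of the SAP's C-SSRS outputs contains a behavior item

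*SAP*

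**What the plan says.** Protocol section 3 lists "Emergent Suicidal behavior using Columbia-Suicide Severity Rating Scale (C-SSRS") among the measures under the primary safety and tolerability objective. SAP 9.1 has the same entry among its primary safety parameters, without the word 'suicidal': "Emergent behavior using Columbia-Suicide Severity Rating Scale (C-SSRS").

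Protocol 9.4.2 commits to C-SSRS listings for all subjects at baseline and at each treatment-period visit, and specifies their content: "The C-SSRS listings will include behavior type and/or category for suicidal ideation and suicidal behavior of the C-SSRS".

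SAP 9.2.7 opens by saying that the scale "will be used to assess suicidal ideation and behavior". It then describes five yes/no ideation items and six intensity items, and derives one score from each group. The planned outputs are by-visit summary statistics of the two scores, a shift table ("A shift table of Suicidal Ideation Items 1 and 2 (Wish to be Dead, Non-Specific Active Suicidal Thoughts) will be presented") and a listing ("A listing of C-SSRS Suicidal Ideation and C-SSRS Intensity of Ideation will be provided"), to which the two scores are added.

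SAP 11 says that the SAP prevails where it and the protocol differ.

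**The concern.** An endpoint named as primary should lead to at least one planned output. Here the link breaks: the parameter is behavior, and everything planned from the instrument is ideation. No reason is given, so it reads as an oversight, but the precedence clause means that following the SAP literally also drops the behavior listing promised in the protocol.

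The population makes this matter. Subjects must have a MADRS total of at least 26 at screening and on Day 1, and Protocol 2.1 itself cites a 15.9% lifetime risk of suicide attempt in this disorder. Exclusions 1 and 2 remove recent attempters and subjects with the more severe ideation responses, so few or no behavior events are to be expected. A documented zero is then the result a reader will look for, and the plan has no output that would show it. Under SAP 5, an analysis added after database lock is labelled post hoc and exploratory, which is an awkward label for a primary safety endpoint.

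**Working it through.** The plan gives no figure to reproduce. The check traces the endpoint to its outputs and then counts what falls outside them.

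**Items defined in SAP 9.2.7.** Ideation 5 + intensity 6 = 11. Behavior: 0.

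**Outputs in SAP 9.2.7.**

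| Output | Content | Behavior included? |
|---|---|---|
| Summary statistics by visit | Ideation score, intensity score | No |
| Shift table | Ideation items 1 and 2 (2 of 5) | No |
| Listing | Ideation and intensity items, two scores | No |

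**Could another part of the SAP supply it?**
- SAP 9 lists safety results only as its relevant section describes, which leads back to 9.2.7. SAP 5 and SAP 10 likewise tie listing content to what the SAP indicates.
- SF-36, HAMD-6, GAD-7, wearable data and biomarkers are expressly sent to separate analysis plans. The C-SSRS is not.
- The free-text event description mentioned in 9.2.7 is a feature of the form, not an output.

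**Behavior assessments with no output (maxima).** Inputs: up to 20 subjects (SAP 6.1) and the C-SSRS visits in the Schedule of Events.
- Treatment period, Days 8, 15, 29, 43 and 56: 5 × 20 = 100. Protocol 9.4.2 commits to listing these.
- Follow-up, Day 70: 1 × 20 = 20. The protocol collects these but does not commit to listing them.
- SAP 4 mentions two subjects discontinued early. Assuming 20 were enrolled and each of the two gave only an early-termination form in the treatment period, 100 becomes 18 × 5 + 2 = 92.

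These are counts of forms, not of expected events.

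**Does adverse event reporting fill the gap?** Protocol 8.4.3 states: "All AEs will be recorded from study drug administration on Day 1 until Day 112". SAP 9.2.1 restricts the tables: "AEs with an onset day after the last day study medication was applied will not be considered TEAEs". With the last dose on Day 56 as scheduled, Days 57 to 112 fall outside the TEAE tables: 112 − 57 + 1 = 56 days. Of these, Days 57 to 70 (70 − 57 + 1 = 14 days) are the interval covered by the Day 70 form. Behavior starting in those 14 days would be in no C-SSRS output and no TEAE table. It could appear only in the AE and SAE listings.

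**Shift table (secondary).** A subject already positive on items 1 and 2 at baseline who moves to items 3, 4 or 5 is shown as unchanged. The rise would still be visible in the by-visit maximum of the ideation score and in the listing. What is missing for ideation is a count of subjects who worsened relative to baseline.

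**The case against.** The strongest reply has four parts.

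- **Little hangs on it.** This is a single-arm study of up to 20 subjects with no formal hypothesis testing, the C-SSRS entry is one of eight unranked safety measures, and no estimate changes. That is true, and it is why the repair is small. It does not give the endpoint an output.
- **Silence is not exclusion.** Where this SAP means to withhold an output it says so, as for the SCID-5-CT and the secondary ophthalmic readings. Its silence on behavior could leave the protocol's listing commitment standing. This is a fair reading of SAP 11, but a programmer working from 9.2.7 would still produce a listing without behavior. The table shells are kept outside the SAP and cannot be seen here. They may contain more, but that would not be a pre-specified commitment.
- **Adverse events will catch it.** The AE and SAE listings are not limited to treatment-emergent events, and serious acts should reach them. This stands in part. Under Protocol 8.4.1.1 and 8.4.1.2, whether a questionnaire finding becomes an AE depends on investigator judgement, and expected manifestations of the disorder under study are not AEs. An AE listing also does not report the C-SSRS endpoint.
- **The remedy exceeds the protocol.** Protocol 9.4.2 promises only a listing, and only for baseline and the treatment period. Correct: the summary table and the Day 70 extension go beyond that text. They are recommended because the endpoint is primary and the Day 70 form is collected anyway.

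The ideation shift table is a lesser matter and carries no weight in the conclusion.

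**Conclusion.** The concern holds, with high confidence. A primary safety endpoint has no planned output from the instrument named to measure it: 0 of 11 defined items and 0 of 3 output types concern behavior. This departs from Protocol 9.4.2 without explanation. The conclusion rests on the text alone. The form counts (at most 100 in the treatment period, plus 20 at Day 70) assume full enrollment and attendance, the figure of 92 rests on the stated assumption about two subjects, and the 56- and 14-day windows assume a last dose on Day 56. The conclusion depends on none of these. It should be corrected before database lock.

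**What to change.** Revise SAP 9.2.7 as follows.

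1. Add all C-SSRS suicidal behavior items to the by-subject listing for baseline and the treatment period, as Protocol 9.4.2 already states, and extend the listing to Day 70.
2. Add one table of n (%) of subjects in the safety population with any post-baseline suicidal behavior. State which pre-dose form and which recall window decide that behavior is emergent.
3. Optional: add n (%) of subjects with post-baseline ideation item 4 or 5, or a shift from the baseline maximum ideation category (0 to 5) to the worst post-baseline category. Name the reference. Under SAP 5.2 it would be the Day 1 pre-dose form, whose recall runs back to screening. Show the screening past-month response separately, because its window differs.

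The cost is SAP wording, one longer listing and one or two small tables. The C-SSRS is already administered at every visit concerned, so no new assessments are needed.
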